## **4. STUDY PROCEDURES**

### **4.1 Center Personnel**

Study investigators and support staff will be responsible for obtaining approval from their institutional IRB and ethics committee. They will be responsible for completing case report forms and maintaining patient-level data throughout the duration of the study. All EPs performing ablation procedures must have a minimum of 3 years experience in complex ablation.

### **4.2 Subject Screening and Informed Consent**

All patients who are being considered for enrollment into the clinical trial must be screened by the site investigator or a member of the designated study staff for study eligibility.

Patients must sign the informed consent form prior to randomization or collection of any study data. Once randomized, they will be considered enrolled in the study. The Investigator, Co-Investigator or Research Coordinator and if necessary, any witnesses should sign and date the consent as well. Consented subjects who do not satisfy entry criteria are screen failures and will not be randomized.

### **4.3 Schedule of Visits and Procedures**

All subjects participating in the study should follow the schedule of visits as outlined in the Table provided.

### **4.4 Pre-Ablation**

Subjects shall undergo the items outlined for Pre-ablation / baseline in Table 2.

- Informed Consent
- Inclusion Exclusion Criteria
- Medical History
- TTE (Trans-thoracic echocardiogram). This can be obtained up to six months prior to the procedure to assess EF which is standard prior to ICD implant. An MRI or TEE can be performed in lieu of a TTE
- TEE (Trans-esophageal echocardiogram) required if subject has history of LA or LV clot and recommended if subject has AF with a CHADS score >1
- A CT or MRI is strongly recommended within 3 month prior to the ablation procedure to allow for anatomy fusion
- 12-lead ECG within 6 months prior to the consent visit
- Assessment of current AAD medication
- Assessment of current anti-coagulation medication

### **4.5 Ablation Procedure (Ablation Arm Only)**

#### **4.5.1 Mapping of Ventricular Substrate**

High-density mapping will be performed with NAVX system (Ensite Velocity, St Jude Medical). Multipolar catheters such as duodecapolar multielecrod (Livewire 2-2-2 mm spacing) are strongly encouraged to facilitate high-density mapping.(5) A minimum of 500 points is strongly encouraged for each chamber mapped. Epicardial mapping will be performed at the discretion of the treating physician but is encouraged for patients with ARVC and NICM.

Scar will be defined as regions of low voltage <1.5 mV with dense scar as <0.5mV.

#### **4.5.2 Ablation Approach and Strategy**

Irrigated-ablation technology will be used for mapping and ablation. The choice of the catheter is up to the discretion of the physician performing the procedure. The ablation technique will be targeting of late and abnormal electrograms within scar with prioritization of those with matching pacemaps, multiple exit sites pacemaps, or demonstrated diastolic activation during VT. Slow conduction zones with isochronal crowding entering the latest zone of conduction should be targeted by using an isochronal activation timing display (Isochronal Late Activation Mapping).(6) Activation and entrainment mapping are encouraged if induced VTs are hemodynamically stable. If time allows, homogenization is the goal of the procedure, where all other local abnormal electrograms that demonstrate uncoupling are eliminated.(7)

#### **4.5.3 Procedural Endpoints**

Programmed stimulation is required before the ablation procedure with two cycle lengths (600ms and 400ms up to triple extrastimuli down to VERP or 200 ms). This may be performed through the implanted ICD (NIPS). A VT is considered clinical if there is a morphologic match by 12-lead ECG or intracardiac EGM or has a similar tachycardia cycle length. Left ventricular stimulation within scar should be performed if the patient is noninducible with RV stimulation. Substrate-based ablation strategy targeting abnormal regions of slow conduction can be performed in the event of noninducibility.

The acute procedural endpoint is noninducibility of the targeted clinical VT and elimination of abnormal electrograms within scar. Programmed stimulation will be performed in the same fashion as prior to ablation. Complete noninducibility is encouraged but not required.

#### **4.5.4 ICD Programming**

The ICD will be programmed to disable all therapies during mapping and ablation.

In the Note section of the device, type the following message:

PAUSE-SCD Trial subject. Please contact [physician or coordinator name] at [center name] at [center phone] before making any programming changes.

Protocol-mandated programmed settings should be confirmed after the device is enabled at the conclusion of ablation. VF zone of 230 bpm (ATP during charging) and VT zone 185 or 10 bpm slower than clinical VT (induced or spontaneous) with detection at 30/40 intervals. (ATPx3).

#### **4.5.5 Data Collection during Ablation**

An ablation procedure form shall be completed by the operator, which includes patient demographics, number of VTs induced and targeted, predominant strategy, number of VT morphologies terminated during ablation, duration of radiofrequency applications, hemodynamic toleration during VT, and scar location and size.

#### **4.5.6 Epicardial Mapping and Ablation**

Epicardial access is encouraged in patients with ARVC and NICM substrate through the subxiphoid percutaneous approach, provided that surgical backup is present at the time of the ablation. This can be performed as a combined strategy, where access is obtained prior to any systemic anticoagulation or after reversal of anticoagulation (documentation of ACT<150) if VT remains inducible after endocardial ablation. It is recommended to leave in an epicardial drain if >50 cc of bleeding is encountered. Coronary angiography is required prior to ablation to detail coronary artery proximity to ablation lesion set as well as high output pacing to assess for phrenic nerve location.

### **4.6 Pre-Discharge**

#### **4.6.1 Pre-Discharge Evaluation**

It is recommended that all patients have overnight observation after ablation. In patients that undergo epicardial ablation, an echocardiogram should be performed in the following day.

Subjects shall undergo the following at Pre-Discharge:

- 12-lead ECG
- Assessment of AAD medication
- Assessment of anti-coagulation medication
- Assessment of Adverse Events

For ICD programming, the following steps will be followed:

- 1) Program the device per guidelines outlined: VF zone of 230 bpm (ATP during charging) and VT zone 185 or 10 bpm slower than clinical VT (induced or spontaneous) with detection at 30/40 intervals. (ATPx3).
- 2) If the device is not programmed according to the settings recommended and unless at discretion of the physician for subject's benefit, a Deviation Form and any other applicable forms (i.e. Adverse Event or Hospitalization Form) must be completed if not previously submitted.
- 3) Print out the following reports to be included with procedure form:
  - i. Wrap-Up Overview

## ii. Parameters Printout

### 4.6.2 Concomitant Medical Therapy

Subject cardiac medications will be documented and tracked over the duration of the study. All subjects with heart failure should have their heart failure medications optimized including use of beta-blockers and ACE inhibitors. A consult with a heart failure specialist is encouraged especially for optimization of drugs and for diuresis after ablation. Subjects in both the ablation and no ablation arm must be maintained on their pre-procedure anti-arrhythmic drug (AAD) unless clinical events dictate otherwise. Anti-arrhythmic medications after ablation are at the discretion of the treating physician.

Subjects who have significant LV endocardial ablation and have LV dysfunction should receive anticoagulation for four weeks post-procedure per current guidelines. Other subjects with LV endocardial ablation should be considered for ASA. Also any subject who requires anticoagulation for other reasons (e.g. AF) should be maintained on therapeutic anticoagulation.

## 4.7 Follow-Up

Follow-ups will be scheduled according to the Table provided:

Study Activity	Baseline	Procedure	3 m	6 m	12 m	18 m	24 m	30m	36m	Unscheduled
Informed Consent	x									
Demographics	x									
Inclusion/Exclusion	x									
Medical History	x									
AAD/Medications	x	x	x	x	x	x	x	x	x	x
TTE	x			x	x		x			
CT/MRI	x									
12 lead ECG	x									
Randomization	x									
ICD implant		x								
Ablation Procedure		x								
ICD Interrogation		x	x	x	x	x	x	x	x	x
Adverse Events										
Death/Withdrawal							x	x		
Protocol Deviations										
Registry Subject	x		x	x	x	x	x	x	x	x

### 4.7.1 Scheduled Visits

The following shall be evaluated at every visit:

- Assessment of AAD medication
- Assessment of anti-coagulation medication

- Assessment of Adverse Events
- ICD Interrogation and event printout
- An Echocardiogram will be performed at 6 months, 1 year, and 2 years if not already performed for routine clinical evaluation.

#### **4.7.2 Unscheduled Visits (as clinically warranted)**

The following shall be evaluated at unscheduled visits:

- Assessment of AAD medication
- Assessment of anti-coagulation medication
- Assessment of Adverse Events
- ICD Interrogation and event printout

To accommodate subject referrals from remote hospitals, follow-up visits and device interrogations may be performed by the referring physician. It is the investigators responsibility to obtain the completed Case Report Forms (CRF).

#### **4.8 Data Collection and Reporting**

All required data, including subject's medical history for this trial are collected on standardized Case Report Forms (CRFs). CRFs were designed to balance the need for comprehensive data collection and to ease the process of data acquisition at the clinical center. The study coordinating site will provide each site with template CRFs to assist with data collection.

Components of the CRF:

- Subject selection criteria
- Medical History
- Medications
- Preoperative baseline subject demographics
- Ablation Procedure forms
- Device Operation Form
- ICD implantation information
- Pre-discharge hospital summary (including post-procedural complications, etc.)
- Assessment data at follow-up
- Adverse event/ Serious adverse event
- Unanticipated Adverse Device Effect
- Report of Death
- Subject Withdrawal
- Protocol Deviations

## 4.9 Source Documentation Requirements

Data recorded on CRFs must be verifiable by source documentation at the research center such as procedure reports, progress notes, discharge summaries, medication logs, and laboratory reports. Each site is responsible for its own data monitoring.

## 5. ADVERSE EVENTS

Adverse events will be monitored and reported in the source documents and on the appropriate case report form, including seriousness, action taken and relationship to investigational system at every visit. If adverse events occur, the first concern will be the safety of the study participants.

### 5.1 Definitions

#### 5.1.1 Adverse Events Definition (AE)

An adverse event is any undesirable clinical occurrence or experience in a subject during the course of the study, whether or not it is related to the device or procedure.

Each adverse event will be classified by the respective site investigator as serious or non-serious. This classification of the event determines the reporting procedures to be followed. The Investigator will also assess the possible relationship between the adverse event and the investigational device. Adverse events will be followed until they are adequately resolved or deemed unresolvable.

#### 5.1.2 Serious Adverse Events Definition (SAE)

A serious adverse event is defined as an adverse event that results in:

- A. Death
- B. Serious deterioration in the health of the subject that:
  - 1) Results in a life-threatening illness or injury;
  - 2) Results in permanent impairment of a body structure or a body function;
  - 3) Requires inpatient hospitalization > 24 hours or prolongation of existing hospitalization;
  - 4) Results in medical or surgical intervention to prevent permanent impairment to body structure or a body function.

#### 5.1.3 Anticipated Adverse Events

The anticipated adverse events provided in section 7.1 (Risks) are believed to represent

adverse events and complications experienced in either animal and/or clinical studies to date with ablation procedures reported in the literature.

#### **5.1.4 Unanticipated Adverse Device Effects (UADE)**

An unanticipated adverse device effect (UADE) is any serious adverse effect on health or safety, any life-threatening problem or death caused by, or associated with, a device, if that effect, problem, or death was not previously identified in nature, severity, or degree of incidence in this Investigational Plan; or any other serious problem associated with a device that relates to the rights, safety, or welfare of subjects. All UADE events should be reported to the coordinating center as soon as possible (within 24 hours), but in no event later than 10 days after the investigator first learns of the event.

### **5.2 Handling and Reporting of Adverse Events**

Adverse events should be recorded in the source documents and on the Adverse Events Form. Non-serious adverse events will be reported to the IRB/EC as required by the respective site's IRB/EC.

If a serious adverse event or unanticipated adverse device effect occurs, the Investigator should do the following:

- 1) Notify the coordinating center within 24 hours of awareness of death, within 48 hours of awareness of a UADE and within 3 business days of awareness of an SAE.
- 2) Obtain and maintain applicable medical records such as procedure summary, diagnostic procedure report, discharge summary, etc. in the treatment and follow-up of the subject.
- 3) Provide the coordinating center a complete case history along with the adverse event form.
- 4) Inform the governing IRB/EC of the serious adverse event, in accordance with the IRB/EC's reporting requirement.

If the site investigator believes that a serious adverse effect is related to study procedures, the coordinating site should be notified within 10 days of the site investigator's knowledge. While the coordinating site will not be responsible for safety conduct at the sites, the study team would like remain aware of any unexpected outcomes or risks.

### **5.3 Subject Death**

Notification of death should include a detailed statement of the pertinent events and be signed by the site investigator in addition to the appropriate CRF(s). It is the site investigator's responsibility to notify the appropriate IRB/EC, in accordance with the

IRB/EC's reporting requirements.

If the site investigator believes that the death is related to study procedures, the coordinating site should be notified within 24 hours of the site investigator's knowledge. While the coordinating site will not be responsible for safety conduct at the sites, the study team would like remain aware of any unexpected outcomes or risks.

Data communicated should include:

- Date of death;
- Primary cause (if known);
- Temporal course of death (if known);
- Any other circumstances surrounding the death;
- Whether it was device or procedure related.
- Autopsy report (if available)

If available, also provide clinical notes and witness statements. Appropriate CRFs must also be completed.

## 6. PROTOCOL DEVIATIONS

A protocol deviation is defined as a study related activity that is not in compliance with the protocol or the Investigator Agreement. Protocol deviations should be tracked and managed by each site, and reported according the site's IRB/EC policies.

Examples of deviations include but are not limited to: a required test not being done or not being done within the specified time-frame, a subject enrolled who did not meet the inclusion/exclusion criteria, a missed follow-up visit or missed visit window or enrollment of a subject without appropriate consent.

## 7. EXPLANATIONS OF RISKS AND MITIGATIONS TO SUBJECTS

### 7.1 Risks

The following complications have been reported for commercially available ablation catheters or in published literature and are expected to be similar to those anticipated in this study. The list of complications includes but is not limited to:

- Death
- Cardiogenic shock
- Complete Heart Block
- New incessant VT/VF
- Acute MI
- Stroke
- Pericarditis
- Cardiac perforation causing pleural effusion or tamponade

- Adverse effects on implantable pacemakers, cardioverters, and defibrillators
- Coronary artery occlusion
- Heart Valve injury
- Acute Pulmonary edema
- Pulmonary embolism
- Vascular access complications
- Phrenic nerve injury
- Arterial/venous thrombus: Clot formation in the artery or vein.
- AV fistula: An abnormal passageway between an artery and a vein.
- Catheter insertion site hematoma
- Hemopneumothorax
- Hypoxia
- Infection: Localized or systemic
- Peripheral venous thrombosis
- Phrenic nerve damage
- Pneumonia
- Pseudoaneurysm
- Radiation injury resulting in dermatitis
- Respiratory failure
- Radiation exposure during the fluoroscopic imaging of the catheters may slightly increase the lifetime risk of developing a fatal malignancy or a genetic defect in offspring
- Fluid overload resulting in pulmonary edema and exacerbation of congestive heart failure (these risks are specific to open irrigated ablation catheters)

Additional risks related to Epicardial Ablation:

- RV puncture
- Pericardial bleeding
- Hemoperitoneum
- Coronary Artery Damage
- Phrenic Nerve Damage
- Pleural Damage
- Myocardial Infarction
- Abdominal Bleeding
- Pericarditis

## 7.2 Mitigation of Risks

Cardiac ablation procedure is performed by physicians thoroughly trained in the technique of VT mapping and radiofrequency catheter ablation, greater than 3 years out of fellowship, have complex ablation experience (typically >50 per year) and in a fully equipped electrophysiology lab. In addition operators and centers should have experience in epicardial ablation. Catheter advancement is carefully performed under fluoroscopic guidance in conjunction with internal electrograms and impedance

monitoring to minimize the risk of cardiac damage. The physician take great care not to use excessive force to advance or withdraw the catheter when resistance is encountered. Since pacemakers and implantable defibrillators can be affected by RF signals, temporary external sources of pacing and defibrillation are available during the ablation procedure. The subject's fluid balance and hemodynamic status is continuously monitored during ablation. Various displays and alarms are used as precautionary measures to warn the physician of the possibility of any undesirable event occurring.

### **7.3 Potential Benefits**

The major benefit of undergoing treatment with ICD and catheter ablation is the reduction and possible elimination of ventricular arrhythmias that may result in death or ICD therapy and shocks. The information gathered from the study will add to the understanding of the treatment options for subjects with ventricular tachycardia. This knowledge may advance medical science and have a benefit on other subjects with a similar arrhythmia.

## **8. DATABASE AND CONFIDENTIALITY**

Conventional data management processing techniques will be used to by each center as they enter the data. The coordinating site and all participating centers are dedicated to maintaining the confidentiality and privacy of subjects who volunteer to participate in the study. Subject identifiers should be removed from any data that is shared with the coordinating site. Subject identifiers include, but are not limited to: subject's name, social security number / unique identification number, and medical record number. Study documents will identify the subject by a subject study identification number.

## **9. STATISTICAL ANALYSIS**

### **9.1 Sample size and power calculation**

Based on assumptions from the SMASH VT trial and the AVID study, a 50% reduction in events from ablation is projected with a 50% event rate in the control arm at 2 years. 120 patients are required to achieve 80% power to detect a true difference of this magnitude with a two-sided alpha error of 0.05. The primary endpoint is a composite that includes cardiovascular rehospitalization and death, which will increase event rates at an estimated 10%/year, individually.

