ICD therapies have been strongly associated with increased hospitalization and all-cause mortality. As catheter ablation of VT has been demonstrated to decrease recurrent VT and ICD therapies, it is biologically plausible that ablation may have an impact on mortality. A recent multicenter study of 2,061 patients by the International VT Ablation Center Collaboration demonstrated that recurrent VT after catheter ablation was associated with a 7-fold subsequent risk for mortality and across all stages of heart failure, patients that had successful ablation experienced improved survival.(1) Only two randomized studies have been completed to date, SMASH VT (2) and VTACH(3), demonstrating that early preemptive ablation results in statistically significant reduction in subsequent ICD shocks. A trend towards improved survival was seen in the ablation group in SMASH VT.

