### **3.5 Study Design Overview**

[figure not shown]
Based on assumptions from the SMASH VT trial and the AVID study, a 50% reduction in events from ablation is projected with a 50% event rate in the control arm at 2 years. 120 patients are required to achieve 80% power to detect a true difference of this magnitude with a two-sided alpha error of 0.05. The primary endpoint is a composite that includes cardiovascular rehospitalization and death, which will increase event rates at an estimated 10%/year, individually.(1,4)

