### **9.2 Primary Endpoint**

The primary efficacy endpoint is defined as freedom from recurrent VT, cardiovascular rehospitalization, and all-cause mortality through a period of 2 years after the procedure (ablation) or randomization (standard medical therapy). Recurrent VT is defined as any appropriate ICD therapy (shock or ATP) or documented sustained monomorphic VT >30 seconds. Cardiovascular rehospitalization is defined as a hospital admission after the randomized procedure for heart failure, procedure-associated complication, or arrhythmia-related causes during the follow-up period.

Prespecified secondary endpoints include each of the individual components of the primary endpoint. Comparison of the ablation-only registry with the randomized patients will serve as an additional secondary outcome measure.

Prespecified subgroup analysis will be performed for patients with RV cardiomyopathy.

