### **9.3 Primary Endpoint Analysis**

The primary endpoint analysis will be a time to event analysis and account for censored observations for all randomized subjects. Intention to treat analysis will be used for this endpoint; the analysis will be “analyzed as randomized” regardless of the actual treatment patients receive during the follow-up period. Kaplan-Meier (1958) estimates of the primary endpoint and overall survival will be generated along with 95% confidence intervals for the median time to event or death (Brookmeyer and Crowley, 1982).(8,9) Log-rank test will be used to compare the hazard functions between the two groups. Cox (1972) regression models will be fit to assess and adjust for baseline covariates.(10) The median time to VT recurrence as well as the 95% confidence intervals will be reported for both groups. The event free survival probability as well as the 95% confidence intervals at the 24-month follow-up for both groups will be presented. Adverse events will be tabulated by type and level of severity and compared between groups using chi-square or Fisher exact tests.

Secondary analyses comparing outcomes in the ICD+ablation and ICD arms vs. the registry patients (ablation only) will be performed in a similar manner to those described above.

Interim analyses will be generated by the coordinating center annually. A Peto-Haybittle efficacy monitoring boundary will be used: if the p-value for the difference between groups is <0.001, early stopping of the trial will be considered. Using this monitoring bound, the p-value for statistical significance at the final analysis will remain at the nominal 0.05 level.

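### Does the 80% power claim in Sections 3.5 and 9.1 fail because the composite's event rates and power are not stated?

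*Combined protocol and SAP*

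**What the plan says.** Sections 3.5 and 9.1 carry the same sample-size paragraph. The planning assumption is that "a 50% reduction in events from ablation is projected with a 50% event rate in the control arm at 2 years", and from this "120 patients are required to achieve 80% power to detect a true difference of this magnitude with a two-sided alpha error of 0.05". The Protocol Summary splits the 120 into 60 per arm. The paragraph closes by noting that the primary endpoint is a composite that includes cardiovascular rehospitalization and death, "which will increase event rates at an estimated 10%/year, individually".

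Section 9.2 defines the primary endpoint as freedom from recurrent VT, cardiovascular rehospitalization and death from any cause through 2 years. Rehospitalization means admission "for heart failure, procedure-associated complication, or arrhythmia-related causes during the follow-up period". Section 9.2 adds: "Prespecified secondary endpoints include each of the individual components of the primary endpoint". Section 9.3 sets the primary comparison: "Log-rank test will be used to compare the hazard functions between the two groups". No section gives a composite rate for either arm, an assumed effect on the added components, a target number of events, or a power figure labelled as applying to the composite.

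**The concern.** The closing sentence of the paragraph can be read as adding events to the 50%. On that reading the 50% is a VT rate, and the 80% describes 50% against 25% for VT, while the primary test is on a composite with more events. More events do not guarantee more power. Events that ablation does not alter pull the composite hazard ratio toward 1, and that can outweigh the gain in event count.

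The 80% is the only power figure in the plan. If it belonged to a different endpoint from the one tested, someone reading a null primary result would not know how likely the trial had been to detect the projected effect. The pilot label is not a full answer, because Section 2.2 says the aim is to show a superior outcome and Section 9.1 makes a formal power statement.

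**Working it through.** **Inputs from the documents.** Control rate 50% at 2 years; 50% reduction; two-sided alpha 0.05; 80% power; 60 per arm; 10% a year for each added component; log-rank test.

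**The plan's own figure.** A 50% reduction in risk gives 25% in the ablation arm.

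- Proportions, pooled variance: mean rate 0.375, so n per arm = [1.96 × √(2 × 0.375 × 0.625) + 0.842 × √(0.25 + 0.1875)]² / 0.25² = 57.7. That rounds to 58 per arm, or 116 in total. Power at 60 per arm is 81.6%.
- Log-rank: HR = ln 0.75 / ln 0.50 = 0.415, and expected events = 60 × (0.50 + 0.25) = 45. Schoenfeld: Φ(|ln 0.415| × √45 / 2 − 1.96) = Φ(2.95 − 1.96) = 83.9%. Freedman: 79.2%, needing 46 events, or 46 / 0.375 ≈ 123 patients for 80%.
- Reading the 50% as a halved hazard does not reproduce the plan: 50% against 29.3%, 47.6 events, 66.7% power, about 166 patients. The reduction is therefore in risk.

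The 120 patients and the 80% stand for 50% against 25%.

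**The composite.** All cases use 60 per arm, no loss to follow-up and Schoenfeld's formula, with HR = ln(1 − pa) / ln(1 − pc) and events = 60 × (pc + pa), where pc and pa are the 2-year control and ablation rates.

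*If the 50% is already the composite rate* and the reduction applies to it, the calculation is the one above and about 80% stands.

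*If the 50% is VT alone and the components are independent* (an assumption), each added component leaves 0.9² = 0.81 event-free at 2 years. Then pc = 1 − 0.50 × 0.81 × 0.81 = 67.2%, and power depends on the assumed effect:

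| Assumed effect of ablation | Ablation composite | HR | Events | Power |
|---|---|---|---|---|
| VT risk halved, nothing else | 1 − 0.75 × 0.6561 = 50.8% | 0.636 | 70.8 | 47.7% |
| VT and rehospitalization risk halved, death unchanged | 1 − 0.75 × 0.905 × 0.81 = 45.0% | 0.537 | 67.3 | 72.3% |
| Composite hazard halved | 1 − √0.328 = 42.7% | 0.500 | 66.0 | 80.4% |
| Risk of every component halved | 1 − 0.75 × 0.905² = 38.6% | 0.437 | 63.5 | 90.9% |
| Composite risk halved | 33.6% | 0.367 | 60.5 | 97.3% |

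*If the added rates are simply summed*, with no effect of ablation on them:

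- 20 points per component: 90% against 65%, HR 0.456, 93 events, power 96.6% (91.7% by proportions).
- 20 points in all: 70% against 45%, HR 0.497, 69 events, power 82.8% (79.9% by proportions).

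Simple addition ignores overlap between components, so it is crude, but the wording allows it.

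**VT alone.** If the 50% is the VT rate, halving it keeps about 80% power. If the 50% is the composite, the VT rate under the same independence model is 1 − 0.50 / 0.6561 = 23.8%. Halved to 11.9%, this gives HR 0.466, 21.4 events and about 42% power. If ablation changed only VT on that reading, the composite would fall from 50% to 42%, with 14% power, but that contradicts the plan's projected 50% reduction.

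**The case for a change.** The strongest case for a change is that the paragraph itself raises the added events and then stops. The phrase about increasing event rates has little function unless the 50% is VT alone. On that reading, with independent components and no effect on the added events, power for the primary test is about 48%. Heart failure and procedure-complication admissions count toward the composite, and death is from any cause, so some dilution is plausible. Two reworded paragraphs would settle the matter at almost no cost.

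Part of this stands. The documents do not say which endpoint the 50% describes, and nothing elsewhere supplies composite rates or component effects. Stating them would make the plan easier to read.

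The rest does not carry. The paragraph projects a reduction in events, not in VT alone, and Section 3.1 gives prevention of the whole composite as the objective. Section 2.1 says that "ICD therapies have been strongly associated with increased hospitalization and all-cause mortality", and the rehospitalization definition includes arrhythmia admissions, so a zero effect on the added components is not what the plan expects. The closing sentence can equally be read as a cushion above the 80%. No single range summarizes the possibilities, because the results run from 14% to 97% according to assumptions that the sponsor did not make. Printing such figures would not tell the reader what was planned.

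**Conclusion.** No change is needed. The stated 120 patients and 80% power reproduce for 50% against 25% (79% to 84%, by method). They also hold for the primary endpoint if the 50% reduction is taken to apply to the composite risk: about 80% at a 50% control rate and 97% at 67%. The 48% figure needs three things together: the 50% being VT alone, independent components, and no effect of ablation on rehospitalization or death. The first is one reading of the text; the other two are outside assumptions, as are full 2-year follow-up and Schoenfeld's approximation.

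What is missing is a label on a planning assumption. It touches neither the randomization, the endpoint, the log-rank test nor its type I error. A null result would be read from the event-free probabilities at 24 months and their 95% confidence intervals, which Section 9.3 already provides for each arm, and not from planning power. The trial is described as a pilot and its current text is already requesting extra follow-up time, so a restated power figure would alter nothing in its conduct or analysis.
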